**2. Primary Protocol Synopsis**

\*For subjects enrolled during protocol Versions A-C. All new subjects will be enrolled under the protocol in Appendix A.

COMBO Study A Study to Demonstrate the Value of Multiple Modalities and Combining Mechanisms using the Spectra WaveWriter™ Spinal Cord Stimulator System in the Treatment of Chronic Pain	
Primary Objective	To evaluate the effectiveness of Spinal Cord Stimulation (SCS) with multiple modalities as compared to conventional SCS in patients with chronic pain when using the Boston Scientific Spectra WaveWriter SCS System.
Secondary Objectives	To determine the impact of Spectra WaveWriter SCS System on global patient outcomes including quality of life, patient preference, etc.
Indication(s) for Use	The Spectra WaveWriter Spinal Cord Stimulator (SCS) System is indicated as an aid in the management of chronic intractable pain of the trunk and/or limbs, including unilateral or bilateral pain associated with the following: failed back surgery syndrome, Complex Regional Pain Syndrome (CRPS) Types I and II, intractable low back pain and leg pain.
Commercial Device/System	BSC Spectra WaveWriter™ SCS System
Study Design	Prospective, multi-center, parallel-group randomized controlled trial with an adaptive design
[REDACTED]	[REDACTED]
[REDACTED]	[REDACTED]

COMBO Study A Study to Demonstrate the Value of Multiple Modalities and Combining Mechanisms using the Spectra WaveWriter™ Spinal Cord Stimulator System in the Treatment of Chronic Pain	
Safety Parameters	Rates of occurrence of all device hardware, device stimulation and procedure related non-serious adverse events, all serious adverse events, and unanticipated adverse events through the end of the study.
Primary Effectiveness Endpoint	Proportion of subjects with 50% or greater reduction from Baseline Visit in average overall pain intensity at 3 months post-randomization, with no increase in baseline average daily opioid medications used to treat pain.
[REDACTED]	[REDACTED]
[REDACTED]	[REDACTED]

COMBO Study A Study to Demonstrate the Value of Multiple Modalities and Combining Mechanisms using the Spectra WaveWriter™ Spinal Cord Stimulator System in the Treatment of Chronic Pain	
Follow-up Schedule	Study events occur at the following time points: 
 
• Screening
 
• Opioid Medication Lock Visit ( Up to 35 days following Informed Consent)
 
• Baseline Period (14 days)
 
• Baseline Visit (0 - 7 days post Baseline Period)
 
• Implant Procedure s (up to 90 days post Baseline Visit)
 
• Healing Period (0 - 28 days)
 
• Randomization Visit (Day 0)
 
• Programming Lock Visit (70 - 14 days post-random ization Visit)
 
• 3 Month Visit (90 + 14 days post-randomization Visit)
 
• 6-Month Visit (180 ± 30 days post-randomi zation Visit)
 
• 9-Month Visit (270 ± 30 days post-randomization Visit)
 
• Year 1 Visit (365 ± 30 days post-random iz ation Visit)
 
• Year 2 Visit (730 ± 30 days post-random iz ation Visit)
 

[REDACTED]	[REDACTED]
[REDACTED]	[REDACTED]
Inclusion Criteria	IC I. Chronic pain of the trunk and/or limbs for at least 6 months with back pain greater or equal to leg pain. [REDACTED] [REDACTED] [REDACTED]

**COMBO Study**

**A Study to Demonstrate the Value of Multiple Modalities and Combining Mechanisms using the Spectra WaveWriter™ Spinal Cord Stimulator System in the Treatment of Chronic Pain**

[Redacted text block]

IC9. 22 years of age or older when written informed consent is obtained

[Redacted text block]

IC11. Able to independently read and complete all questionnaires and assessments provided in English

[Redacted text block]

IC13. Subject signed a valid, IRB-approved informed consent form (ICF) provided in English

**Exclusion Criteria**

[Redacted text block]

**COMBO Study**

**A Study to Demonstrate the Value of Multiple Modalities and Combining Mechanisms using the Spectra WaveWriter™ Spinal Cord Stimulator System in the Treatment of Chronic Pain**

[REDACTED]

EC7. Any pain-related diagnosis or medical/psychological condition that, in the clinician's best judgment, might confound reporting of study outcomes (e.g. pelvic pain, anginal pain, chronic migraine, brain or spinal cord tumor)

[REDACTED]

EC15. Significant cognitive impairment at Screening that, in the opinion of the Investigator, would reasonably be expected to impair the study candidate's ability to participate in the study

EC16. Participating (or intends to participate) in another drug or device clinical trial that may influence the data that will be collected for this study

[REDACTED]

EC18. A female who is breastfeeding

EC19. A female of childbearing potential planning to get pregnant during the course of the study or not using adequate contraception

[REDACTED]

COMBO Study A Study to Demonstrate the Value of Multiple Modalities and Combining Mechanisms using the Spectra WaveWriter™ Spinal Cord Stimulator System in the Treatment of Chronic Pain	
	
[REDACTED]
 
[REDACTED]
 
[REDACTED]
 
[REDACTED]
 
[REDACTED]
 
EC23. [REDACTED]

Statistical Methods	
Primary Statistical Hypothesis	
The primary statistical hypothesis in this study is that the proportion of subjects with 50% or greater reduction from Baseline Visit in average daily overall pain in intensity at 3 months post randomization in the WaveWriter group is non-inferior compared to the Control (i.e. Conventional) group
 $H_0: \pi_{TW} - \pi_C \leq -0.20$ $H_1: \pi_{TW} - \pi_C > -0.20$ 
Where <math>\pi_{TW}</math> and <math>\pi_C</math> are the proportion of subjects with 50% or greater reduction from Baseline in average daily overall pain in intensity at 3 months post randomization with no increase in baseline average daily opioid pain medications using Spectra WaveWriter all modalities and conventional settings, respectively. The study's non-inferiority margin is 0.20.

[REDACTED]	[REDACTED]
[REDACTED]	[REDACTED]

COMBO Study

A Study to Demonstrate the Value of Multiple Modalities and Combining Mechanisms using the Spectra WaveWriter™ Spinal Cord Stimulator System in the Treatment of Chronic Pain

	
[REDACTED]
 
[REDACTED]
 
[REDACTED]
 
[REDACTED]
 
[REDACTED]
 
[REDACTED]


[REDACTED]
	
[REDACTED]
 
[REDACTED]
 
[REDACTED]
 
[REDACTED]
 
[REDACTED]

g  
f

g

g

g

g  
f

SAOOIS<H3N1.1

--	--	--	--	--	--	--

dn M OHIO:i w Ja l 8uo1	JeUOII U81UO)	:X	3 "ii. ii. >> >>	III S. t.	II. S. OQ
	J8 I:JM8 11eM	6.0.1.7	f- t. -	0. c.	

>MPO0EE  
0 1 d/l >MJ>06 Ol d/l >MP +t SMPSC Ol d/l

## 4. Introduction

### 4.1. *Chronic Intractable Pain*

Chronic intractable pain is often defined as pain persisting for at least 6 months which has not responded to conservative treatment(s). The pain may be due to current or past nerve injury and causes significant disability, reduced work productivity, reduced quality of life, and significant cost burden.

The complexity of chronic pain and the diverse population it affects have resulted in varying results between the various treatment approaches including medications, physical therapy, stimulation etc. Early treatments for chronic pain typically include over the counter and prescription medications. Later treatments like physical therapy and interventional pain procedures (e.g. intraspinal injections, vertebroplasty, pulsed radiofrequency (RF) are attempted, sometimes followed by chronic high dose opioids and back surgery, if indicated. If back surgery is unsuccessful in relieving the chronic pain, the patient can be labeled as having failed back surgery syndrome (FBSS). Spinal cord stimulation (SCS) is an option in well-selected patients with chronic low back and/or leg pain.

### 4.2. *Spinal Cord Stimulation*

SCS is effective for chronic intractable pain associated with a variety of conditions, including, but not limited to, FBSS ((Carter et al., 2004, Taylor et al., 2004), complex regional pain syndrome (Sears et al., 2011), and low back pain and leg pain (Cameron et al., 2004). Spinal cord stimulation (SCS) is a less invasive treatment option for FBSS but has generally been reserved for patients who have failed multiple, and indeed all possible, repeat operations. With SCS, an implanted pulse generator (IPG) delivers electrical current to electrode(s) implanted in the epidural space. This current stimulates nerves and can be programmed to direct stimulation to the nerves innervating the painful location, resulting in a reduction of the intensity of that pain (Kumar et al., 2006). Before an SCS system is implanted, a patient often undergoes a screening trial with an electrode that is connected to an external stimulator that the patient wears outside of the body. The results of the screening trial can predict the patient's outcome with an implanted system (Kumar et al., 2006).

In SCS pain relief is realized when the nerves that innervate the painful region(s) are electrically stimulated (North et al., 1990). To increase the chance of success, the electrode contacts are programmed based on the patient feedback to various combinations of contact polarities (anodes and cathodes), pulse rate (or frequency), pulse amplitude (or current), and pulse width.

Traditionally, Spinal Cord Stimulation (SCS) has relied on the understanding that to achieve pain relief, dorsal column stimulation-induced paresthesia has to be generated around the area of pain in order to successfully treat pain (North et al. 1991). However, recent studies indicate that effective pain relief may be obtained by employing stimulation without paresthesia (Van Buyten et al., 2012, De Ridder et al., 2010, Kapural et al 2015).

## **5. Commercial Device Description (part of Standard of Care)**

The Spectra WaveWriter™ Spinal Cord Stimulator (SCS) System is indicated as an aid in the management of chronic intractable pain of the trunk and/or limbs, including unilateral or bilateral pain associated with the following: failed back surgery syndrome, Complex Regional Pain Syndrome (CRPS) Types I and II, intractable low back pain and leg pain.

The System includes an Implantable Pulse Generator (IPG), External Trial Stimulator (ETS), Remote Control (RC), External Charger, and Clinician's Programmer (CP) and a portfolio of lead options. The IPG is rechargeable and is recharged transcutaneously by a charging unit. The System is capable of providing multiple waveforms.

The Spectra WaveWriter™ SCS System is approved by the Food and Drug Administration (FDA) and will be used per approved Directions for Use (DFU) in this study.

## **6. Study Objectives and Endpoints**

### ***6.1. Primary Objective***

The primary objective of this study is to evaluate the effectiveness of Spinal Cord Stimulation (SCS) with multiple modalities as compared to conventional SCS in patients with chronic pain when using the Boston Scientific Spectra WaveWriter SCS System.

### ***6.2. Secondary Objective***

The secondary objective of this study is to determine the impact of Spectra WaveWriter SCS System on global patient outcomes including quality of life, patient preference, etc.

### ***6.3. Primary Endpoint***

The primary endpoint is the proportion of subjects with 50% or greater reduction from the Baseline Visit in average overall pain intensity at 3 months post randomization, with no increase in baseline average daily opioid medications used to treat pain.

[REDACTED]

[REDACTED]

[REDACTED]

[REDACTED]

[REDACTED]

[REDACTED]

**6.6. Safety Parameters**

[figure not shown]
Safety parameters include the rates of occurrence of all device hardware, device stimulation and procedure related non-serious adverse events, all serious adverse events, and unanticipated adverse events through the end of the study.

**7. Study Design**

The study is a prospective, multi-center, parallel group randomized controlled trial with an adaptive design. All participants will receive the Spectra WaveWriter Spinal Cord Stimulator (SCS) system and followed per the study schedule as shown in study schematic Figure 8.1-1.

[REDACTED]

Figure 7.1-1: COMBO Study Design

### 7.2. Treatment Assignment

All enrolled subjects who pass eligibility criteria will receive a trial. Subjects with a positive trial will proceed to receive permanent implant. Following permanent implant, all subjects' device will be randomized in a 1:1 ratio to either receive:

- WaveWriter Settings – Perception and/or sub-perception programming with all available modalities
- Conventional Settings – Perception programming (up to 1.2 kHz)

### 7.3. Justification for the Study Design

The study is a prospective, multi-center, parallel group randomized controlled trial with an adaptive design. The study is designed to demonstrate the value of multiple modalities and combining mechanisms for sustained clinically significant pain relief in patients with chronic pain when using the Boston Scientific Spectra WaveWriter SCS System. Additionally, the impact of the Spectra WaveWriter SCS System on global patient outcomes, quality of life and patient preference will also be evaluated.

A prospective study design will eliminate the bias associated with case selection in a retrospective review and will ensure that identical procedures are followed for data capture and review.

A multi-center design will minimize the impact on treatment outcome that may potentially result from differences in patient selection, regional differences in the patient demographic, and differences in investigator technique and patient management.

The study design includes two groups (arms) – WaveWriter group and Conventional group. The WaveWriter group will receive all the programming capabilities available in the WaveWriter SCS System while the conventional group will have limited programming capabilities. The Conventional group will serve as a control in this study. Randomization (1:1) will minimize selection bias and impact of demographic variables.

The primary endpoint is the proportion of subjects with 50% or greater reduction (responder rate) from the Baseline Visit in average overall pain intensity at 3 months post-randomization, with no increase in baseline average daily opioid medications used to treat pain. A 3-month endpoint was chosen as 3 months provides adequate time for a subject to have their programming parameters optimized.

## **8. Subject Selection**

### **8.1. Study Population and Eligibility**

Study candidates will be drawn from the population of patient's resident in pain management or surgical medical practices. The study eligibility criteria are listed below.

### **8.2. Inclusion Criteria**

Subjects who meet all of the following criteria (see Table 8.2-1) may be given consideration for inclusion in this clinical investigation, provided no exclusion criterion (see Section 8.3) is met.

**Table 8.2-1: Inclusion Criteria**

Clinical Inclusion Criteria	IC1. Chronic pain of the trunk and/or limbs for at least 6 months with back pain greater or equal to leg pain.
	[REDACTED]
	[REDACTED]
	[REDACTED]
	[REDACTED]
	[REDACTED]
	[REDACTED]
	[REDACTED]
	[REDACTED]
	[REDACTED]
IC9. 22 years of age or older when written informed consent is obtained	
[REDACTED]	
[REDACTED]	
IC11. Able to independently read and complete all questionnaires and assessments provided in English	
[REDACTED]	
[REDACTED]	
IC13. Subject signed a valid, IRB-approved informed consent form (ICF) provided in English	

**8.3. Exclusion Criteria**

Subjects who meet any one of the following criteria (**Error! Reference source not found.**) cannot be included in this study or will be excluded from this clinical study.

**Table 8.3- 1 Exclusion Criteria**

---

Clinical Exclusion Criteria	
[REDACTED]
 
[REDACTED]
 
[REDACTED]
 
[REDACTED]
 
[REDACTED]
 
[REDACTED]
 
[REDACTED]
 
[REDACTED]
 
[REDACTED]
 
EC7. Any pain-related diagnosis or medical/psychological condition that, in the clinician's best judgment, might confound reporting of study outcomes (e.g. pelvic pain, anginal pain, chronic migraine, brain or spinal cord tumor)
 
[REDACTED]
 
[REDACTED]
 
[REDACTED]
 
[REDACTED]
 
[REDACTED]
 
[REDACTED]
 
[REDACTED]
 
[REDACTED]
 
[REDACTED]
 
[REDACTED]
 
[REDACTED]
 
EC15. Significant cognitive impairment at Screening that, in the opinion of the Investigator, would reasonably be expected to impair the study candidate's ability to participate in the study
 
EC16. Participating (or intends to participate) in another drug or device clinical trial that may influence the data that will be collected for this study
 
[REDACTED]
 
[REDACTED]
 
EC18. A female who is breastfeeding
 
EC19. A female of childbearing potential planning to get pregnant during the course of the study or not using adequate contraception

-----------------------------	--

	
[REDACTED]
 
[REDACTED]
 
[REDACTED]
 
EC23. [REDACTED]

--	---

## 9. Subject Accountability

### 9.1. Point of Enrollment

A subject will be considered enrolled in the study when the Informed Consent Form (ICF) is signed. All enrolled and randomized subjects will be included in the study analyses.

If device implantation is unsuccessful, the subject will be followed for 2 weeks post implantation attempt to assess for procedure related adverse events.

### 9.2. Withdrawal

All subjects enrolled in the clinical study (including those withdrawn from the clinical study) shall be accounted for and documented. If a subject withdraws from the clinical investigation, the reason(s) shall be reported. If such withdrawal is due to problems related to device safety or performance, the investigator shall ask for the subject's permission to follow his/her status/condition outside of the clinical study.

While study withdrawal is discouraged, subjects may withdraw from the study at any time, with or without reason and without prejudice to further treatment. In all cases of withdrawal or discontinuation, the Investigator will make all reasonable efforts to determine the reason for the subject's withdrawal. Subjects may be discontinued from the study for the various reasons, such as:

- Withdrawal of consent
- A safety concern defined by the Principal Investigator and/or Boston Scientific Neuromodulation (e.g., adverse event)
- Study non-compliance
- Inadequate use of device that may impact study outcomes
- Subject did not meet inclusion criteria or met an exclusion criterion after signing informed consent

- Surgical intervention that affects the Implantable Pulse Generator (IPG) and/or leads
- Lost to follow-up
- Death of the subject

A subject is considered lost-to-follow-up after 3 unsuccessful contact attempts have been made to reach the subject (including those who relocate but cannot be transferred to another participating site). Staff at the participating site should make a good faith effort to contact the subject with three documented communication attempts, at least one of which must be in writing, sent via a traceable method to inform the subject that the device must be programmed per standard of care with commercially approved settings.

Data collected up to the point of subject withdrawal or lost to follow-up may be used for study analysis in accordance with applicable regulations.

Withdrawn subjects will be followed per the End of Study Action Plan as described below.

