### ***9.5. End-of-Study Action Plan***

When each subject completes the 2-Year Visit or withdraws, the subject exits the study and ends study participation. Subjects may continue to use their system per the applicable Directions for Use and will be followed according to standard of care. Boston Scientific Neuromodulation Corporation will not pay for visits, devices and/or procedures that occur after a subject completes the 2-Year Visit, withdraws or is determined to be lost to follow-up with the exception of the explant procedure. Reimbursement for the explant procedure will be covered by Boston Scientific if performed within 2 months from the end of study date.

If the study is terminated early due to sponsor discretion or due to the discovery of an unexpected, significant, or unacceptable risk/safety concern regardless of how far along the subject has reached in their study follow-up, subjects will be followed according to standard of care. Sites will have 30 days to notify all subjects of study closure.

If device implantation is unsuccessful, the subject will be followed for 2 weeks post implantation attempt to assess for procedure related adverse events. If the device is explanted, the subject will be followed for 30 days post explant to assess for related adverse events.

Device related adverse events and/or deficiencies occurring after study participation, withdrawal from the study, or after the specified timeframe following unsuccessful trials, implant failures, and explants, should be reported to BSN Patient Care at: [contact]. Such complications should not be captured as adverse events in the study.

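### Randomised subjects can be discontinued from the study before month 3 with no visible provision for collecting the primary outcome, although the ITT analysis decides success

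*Combined protocol and SAP*

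**What the plan says.** Section 9.2 discourages withdrawal but gives an open list of reasons for which a subject may be discontinued from the study. Besides non-compliance, it names "Inadequate use of device that may impact study outcomes" and "Surgical intervention that affects the Implantable Pulse Generator (IPG) and/or leads". What ends is study participation, and no ground is limited to the period before randomisation.

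On what happens afterwards, the visible text offers:

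- Section 9.2: "Data collected up to the point of subject withdrawal or lost to follow-up may be used for study analysis". If the cause is device safety or performance, the investigator asks for "permission to follow his/her status/condition outside of the clinical study". Subjects being lost to follow-up are to be told in writing that "the device must be programmed per standard of care with commercially approved settings".
- Section 9.5: "When each subject completes the 2-Year Visit or withdraws, the subject exits the study and ends study participation". It adds: "Subjects may continue to use their system per the applicable Directions for Use and will be followed according to standard of care". Sponsor payment for visits stops at withdrawal.
- Section 9.5, for explant: "If the device is explanted, the subject will be followed for 30 days post explant to assess for related adverse events".
- Section 10.17: randomised, implanted subjects are followed to the 2-Year Visit or until they withdraw.

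On the analysis side, section 9.1 includes all randomised subjects, section 9.3 bars their replacement, section 11.2.1 defines ITT as everyone randomised, and section 11.1.1.3 declares success if the lower two-sided 95% limit in the ITT analysis exceeds -0.20. Section 10.15.1 withdraws subjects who refuse a recommended lead revision but counts them in ITT. Those who agree to revision continue on the original schedule.

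**The concern.** The primary endpoint needs a pain value and an opioid value at 3 months. The plan counts every randomised subject in the deciding analysis, while its own rules stop collecting outcomes from some of them who may still be willing and reachable. These gaps are created by the protocol, in addition to those caused by refusal or loss of contact.

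The grounds may also be related to outcome. Little device use, or refusal of a lead revision, is plausible in a subject who gets no relief. This is an inference from the listed grounds, not a demonstrated bias. If loss differs between arms, the non-inferiority conclusion can move either way.

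A separate inconsistency concerns agreed revision or replacement. The surgery ground in 9.2 permits discontinuation, while 10.15.1 says the subject continues. Sites could therefore handle the same event differently. There is no such conflict for explant.

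**Working it through.** **Step 1: does any visible follow-up supply the endpoint?**

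| Follow-up after withdrawal | Section | Gives 3-month pain and opioid outcome? |
|---|---|---|
| Standard of care | 9.5 | No study assessment |
| Status follow-up by permission, device problems only | 9.2 | No, it is outside the study |
| 30 days after explant | 9.5 | No, adverse events only |
| Scheduled visits | 10.17 | Stop at withdrawal |

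None does. The visible text gives no sample size, expected responder rate or dropout rate, so there is no planned figure to reproduce.

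**Step 2: scale, on assumed inputs.** From the protocol: margin 0.20, lower two-sided 95% limit above -0.20 (11.1.1.1, 11.1.1.3), 1:1 allocation (7.2). Assumed: 82 per arm; true responder rates 0.50 (WaveWriter) and 0.70 (control), so the difference is exactly -0.20 and any declared success is false; a Wald interval. The result is the exact binomial probability that the lower limit exceeds -0.20. Loss by month 3 is written WaveWriter v control.

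**(a) Lost subjects are all non-responders and are left out.** With loss fractions wt and wc, the observed rates are 0.50/(1-wt) and 0.70/(1-wc), on 82(1-wt) and 82(1-wc) subjects, rounded.

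- 2% v 2%: 0.50/0.98 = 0.5102 and 0.70/0.98 = 0.7143, 80 per arm, difference -0.204.
- 5% v 0%: 0.50/0.95 = 0.5263 against 0.70, 78 v 82 subjects, difference -0.174.

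| Loss | False non-inferiority |
|---|---|
| none | 2.6% |
| 2% v 2% | 2.1% |
| 5% v 5% | 1.7% |
| 10% v 10% | 1.2% |
| 3% v 1% | 3.1% |
| 5% v 3% | 2.9% |
| 5% v 0% | 5.3% |
| 10% v 0% | 10.9% |
| 0% v 5% | below 1% |

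With 60 to 150 per arm, 5% v 0% gives 4.9% to 6.6%.

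**(b) Missing scored as failure, loss unrelated to response.** Rates become 0.50(1-w) and 0.70(1-w) on 82 per arm. At 5%: 0.475 - 0.665 = -0.190. Results: 2.9% at 2% v 2%, 3.3% at 5% v 5%, 4.1% at 10% v 10%.

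If instead the lost subjects are all non-responders and missing is scored as failure, the rates stay 0.50 and 0.70 and the error stays 2.6%, whatever the loss.

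**(c) Possible cost of the remedy.** Suppose a fraction k of controls discontinue, receive all modalities, respond at the WaveWriter rate and are analysed as randomised. The control rate is 0.70(1-k) + 0.50k.

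| k | Control rate | Difference | False non-inferiority |
|---|---|---|---|
| 2% | 0.696 | -0.196 | 2.9% |
| 5% | 0.690 | -0.190 | 3.5% |
| 10% | 0.680 | -0.180 | 4.6% |

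With 60 to 150 per arm, k = 10% gives 4.1% to 5.4%.

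**The case against.** The best reply is that the harm is conditional. Rules on retained follow-up or missing data may sit in redacted text: after 9.3, after 10.15.1, in 10.11 and in section 11. The larger figures in (a) assume an observed-case analysis that no visible passage states, and they need loss concentrated in the WaveWriter arm, which nothing visible predicts. If lost non-responders are scored as failures, there is no bias. Table 10.1-1 also collects pain relief and opioid data at the Programming Lock Visit, so late discontinuations have a near-endpoint value. The surgery ground in 9.2 is permissive and can be read subject to the specific rule in 10.15.1. The remedy has its own dilution cost, shown in (c). Finally, the synopsis limits this text to subjects enrolled under Versions A-C; new subjects follow Appendix A, which is not visible.

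All of this bears on size, and it is why no size can be claimed. It does not remove the gap. An imputation rule, redacted or not, fills in values; it does not obtain them from subjects who still consent and can be reached. A Programming Lock value is not the 3-month endpoint and does not exist for earlier discontinuations. Scoring as failure is correct only if every lost subject is in fact a non-responder.

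**Conclusion.** The concern holds on the visible text. Sections 9.2, 9.5, 10.15.1 and 10.17 together allow a randomised subject to leave before month 3 without a primary outcome, while 9.1, 11.1.1.3 and 11.2.1 keep that subject in the deciding analysis. The size and direction of any bias are unknown and depend on how many are lost in each arm by month 3. On the assumed inputs, small balanced loss matters little (2.1% at 2% v 2%, against 2.6% with no loss), and one-sided loss can roughly double the error (5.3% at 5% v 0%) or push it below 1% (0% v 5%). The change is worth making because it is cheap and protects the deciding analysis. Confidence is medium, because of the redactions and because the text of Appendix A cannot be seen.

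**What to change.** 1. In 9.2, 9.5 and 10.15.1, distinguish stopping the assigned treatment or programming, on clinical grounds left to the sponsor and investigator, from ending data collection.
2. State that randomised subjects who still consent and can be contacted keep the 3-Month pain and opioid assessments already scheduled, and are analysed as randomised in ITT.
3. Record any change of programming or opioids after discontinuation. Report one sensitivity analysis that treats values obtained after such a change as unknown, varies the number of responders among those subjects over its full range in each arm, and states where the lower 95% limit crosses -0.20.
4. Reconcile the surgery ground in 9.2 with 10.15.1 for revision or replacement the subject agrees to.
5. If redacted sections already contain such rules, cross-refer to them from 9.2. Make the same changes in Appendix A if it carries the same text.

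This alters data collection and analysis only, not care. The cost is wording in three sections, one sensitivity analysis, some tracing, and sponsor payment for one visit, which 9.5 now ends at withdrawal. Dilution towards non-inferiority, as in (c), is possible; the sensitivity analysis exposes it but does not remove it. Subjects under Versions A-C who are already past month 3 gain nothing.
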